7.3.5 Exposure

The following tables show the variables which will be calculated to measure exposure to MOR00208. Details regarding study drug administration are only captured from Cycle 1 to Cycle 3 in the eCRF. In the maintenance treatment phase, the only information which is captured in eCRF at the follow-up visits is whether the patient will continue to receive study drug.

Statistical Analysis Plan Final Version 4.0

Variables calculated for each study drug administration (Cycle 1 to Cycle 3)

Percentage of actual volume administered vs. planned volume [%]	Actual volume administered [mL]/250 mL*100%
Actual dose administered per kg [mg/kg]	(Actual volume administered [mL]/250 mL)*Assigned dose [mg/kg]
Actual dose administered [mg]	(Actual volume administered [mL]/250 mL)*Assigned dose [mg/kg]* Weight[kg] Note: The weight obtained at each visit before study drug administration should be used to calculate the study drug dose for the respective visit. Only in exceptional cases, e.g. due to logistical issues, the weight obtained at the previous visit can be used (provided that there is no obvious change of $\pm 10\%$ compared with the previous visit).

Variables calculated on a per-patient basis:

All of the variables shown in the table below will summarize the exposure from cycle 1 to cycle 3, except the first variable “duration of exposure including maintenance treatment” which will include maintenance treatment.

Statistical Analysis Plan Final Version 4.0

Duration of exposure including maintenance treatment [weeks]
	
Time from Cycle 1, Day 1 to date of last study treatment (approximated) [weeks]
 
Note: This variable can only be approximated as the date of last study treatment is not captured in the eCRF:
 
Date of last study treatment is approximated as follows:
 
 - If patient did not receive maintenance treatment at all, the date of last study treatment is the date of last study treatment entered to the study drug administration page - If patient received (or is planned to receive) maintenance treatment, the date of last study treatment will be approximated as the minimum of the two following: 
 o Date of follow-up visit where the question “Will the subject continue to receive treatment?” is ticked as “NO” for the first time (on the response assessment eCRF page) o End of study date (from study completion page)

Number of cycles with all infusions completed
	
Number of cycles with all 4 infusions completed

Total number of infusions administered
	
Number of all infusions

Total number of infusions administered in Cycle x
	
Number of all infusions in Cycle x

Total number of infusions with a duration > 2.5 h
	
Number of infusions with (sum of all periods (stop time – start time)) > 150 minutes

Statistical Analysis Plan Final Version 4.0

Total number of infusions with a duration > 2 h	Number of infusions with (sum of all periods (stop time – start time)) > 120 minutes
Total number of infusions with a duration of 2 to 2.5 hours	Number of infusions with (sum of all periods (stop time – start time)) >= 120 minutes, but <=150 min
Total number of infusions with a duration of < 2 hours	Number of infusions with (sum of all periods (stop time – start time)) < 120 minutes
Total number of infusions administered with any modification	Number of all infusions with any treatment modification (infusion rate reduced, infusion rate increased, infusion interrupted and restarted, infusion stopped)
Total volume administered [mL]	Sum of the variable “Actual volume administered [mL]” over all infusions
Average percentage of actual volume administered vs. planned volume [%]	Mean of the variable “Percentage of actual volume administered vs. planned volume [%]” over all infusions
Total actual dose administered per kg [mg/kg]	Sum of the variable “Actual dose administered per kg [mg/kg]” over all infusions
Total actual dose administered [mg]	Sum of the variable “Actual dose administered [mg]” over all infusions
Average actual dose administered per kg [mg/kg]	Mean of the variable “Actual dose administered per kg [mg/kg]” over all infusions

8. STUDY PATIENTS AND DEMOGRAPHICS

8.1 Disposition of Patients and Treatment Discontinuation

The following will be summarized by study population (i.e., NHL subtype) for all patients who provided an informed consent for study participation:

CONFIDENTIAL

03 April 2019

AD-ST-33.02 8 April 2011

Statistical Analysis Plan Final Version 4.0

- Number (%) of patients enrolled (defined as having completed the Informed Consent eCRF page)
- Number (%) of patients screened
- Number (%) of screen failures including the reasons for being screen failures
- Number (%) of patients treated (as per IRT information)
- Number (%) of patients who discontinued in Cycle 1 or Cycle 2 (considering all discontinuations during the Cycles including those at the end of Cycle 2, i.e., C2D28), including the reason for discontinuation
- Number of patients who discontinued before completing Cycle 2 including the reason for discontinuation
- Number of patients completing Cycle 2
- Number of patients completing the first 2 Cycles without proceeding to Cycle 3 (i.e., PD or SD at the end of Cycle 2), including the reason for discontinuation
- Number of patients who completed Cycle 2 and entered Cycle 3 (i.e., patients who reached PR, or CR by the end of Cycle 2)
- Number of patients who discontinued in Cycle 3 (considering all discontinuations that happened in Cycle 3 including those at the end of Cycle 3, i.e., C3D28), including the reason for discontinuation
- Number of patients who discontinued in Cycle 1 or 2 or 3 (considering all discontinuations that happened during Cycle 1, 2, 3 including those at the end of Cycle 3, i.e., C3D28), including the reason for discontinuation
- Number of patients who entered the maintenance treatment phase (i.e., treatment after Cycle 3)
- Number of patients who discontinued during the maintenance treatment phase including the reason for discontinuation
-
- Number of patients still on treatment (i.e., ongoing at data cut-off; the information will be derived from entries in the IRT system)
- Number (%) of patients screened, and number (%) of screen failures including the reason for screen failure.

- Number (%) of patients screened, and number (%) of screen failures by center.

These summaries will be presented for the population of screened patients. The disposition summary will additionally be presented for all patients enrolled, including screening failures.

A listing will be provided indicating in which study stage of the trial individual patients were recruited (the listing will be generated based on information in the IRT system).

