Immunogenicity Assessments	
 Number of patients with confirmed positive anti-MOR00208 antibodies MOR00208 antibody titer of confirmed positive samples

Statistical Methods and Data Analysis	The primary efficacy endpoint will be ORR as determined by using revised IWG response criteria for malignant lymphoma. The final ORR for each subtype will be the rate of patients who met the criteria of PR or CR at the end of either the second or third cycle or during a response assessment in the follow-up period (best response). Patients with PD after Day 28 of the second cycle will be discontinued and classified as nonresponders. Those with SD after Day 28 of the second cycle will be allowed to continue treatment into a third cycle.
--	--

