10 VISIT SCHEDULE AND ASSESSMENTS

[Table 2](#) lists all of the assessments, and indicates with an "X" the visits at which these assessments are performed. All data obtained from these assessments must be supported in the patient's source documentation.

Table 2 Schedule of Assessments

Evaluation or Procedure	Screening	Cycle 1 (28 days)					Cycle 2 (28 days)					Cycle 3 (if response is at least SD) (2 weeks ± 1 day after Cycle 2 Day 22)					Follow-up		Maintenance Treatment Visits beyond Follow-up Visit 12 ²⁰	EOS Visit	
		-21 to -1	Day 1	Day 2	8 ± 1 day	15 ± 1 day	22 ± 1 day	1 ± 1 day	8 ± 1 day	15 ± 1 day	22 ± 1 day	28 ± 4 days	1 ± 1 day	8 ± 1 day	15 ± 1 day	22 ± 1 day	28 ± 4 days	1 st Follow-up + 4 weeks ± 2 days			Follow-up Visits 2 - 12 ¹
Informed consent	X																				
Inclusion/exclusion criteria	X	X ²																			
Demography	X																				
Medical history (incl. prior NHL treatments)	X																				
Staging	X																				
ECOG	X	X			X		X		X				X		X			X	X		X
Determination of CD19 on tumor cells (bone marrow)	X																				
Determination of CD19 on tumor cells (tumor biopsy/aspirate) ³	X																				
Study drug administration		X		X	X	X	X	X	X	X		X	X	X	X					X ²⁰	
Premedication		X		X	X	X ⁴	X ⁴	X ⁴	X ⁴	X ⁴		X ⁴	X ⁴	X ⁴	X ⁴						
“Emergency laboratory”		X ¹⁹		X ¹⁹	X ¹⁹	X ¹⁹	X ¹⁹	X ¹⁹	X ¹⁹	X ¹⁹		X ¹⁹	X ¹⁹	X ¹⁹	X ¹⁹						
Haematology	X	X ²	X	X ²	X ²	X ²	X ²	X ²	X ²	X ²	X	X ²	X ²	X ²	X ²	X	X	X	X	X	X
Serum chemistry	X	X ²	X	X ²	X ²	X ²	X ²	X ²	X ²	X ²	X	X ²	X ²	X ²	X ²	X	X	X	X	X	X
Coagulation	X	X ²					X ²					X ²					X	X	X		X
Pharmacokinetics		X ⁵		X ⁶	X ⁶	X ⁶		X ⁶		X ⁶	X		X ⁶		X ⁶	X	X	X ⁷			
Urinalysis	X	X ²					X ²					X ²					X	X			X
β-HCG pregnancy test (WOCBP)	X																X ²²	X ²²			X
Urine pregnancy test (WOCBP)		X ²					X ²					X ²					X ²²	X ²²	X		
Serology (Hepatitis B and C)	X					X ²¹					X ²¹					X ²¹	X ²¹	X ²¹	X ²¹		
B-, T- and NK cell flow cytometry		X ²		X ²	X ²	X ²		X ²		X	X ²		X ²		X						X
CD16 expression on NK cells	X						X ²					X ²					X	X ¹⁸			
Anti-MOR00208 antibodies		X ²					X ²					X ²									
FcγR polymorphism (mucosal cheek swab)		X ²																			

Table 2 Schedule of Assessments

Evaluation or Procedure	Screening	Cycle 1 (28 days)					Cycle 2 (28 days)					Cycle 3 (if response is at least SD) (2 weeks ± 1 day after Cycle 2 Day 22)					Follow-up		Maintenance Treatment Visits beyond Follow-up Visit 12 ²⁰	EOS Visit + 4 weeks ± 2 days	

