10.2 Main Treatment Phase (Cycles 1-3)

Only patients fulfilling all inclusion and none of the exclusion criteria should be enrolled.

The schedule of required procedures for each treatment day is detailed in [Table 2](#). Clinical site study days are Days 1, 2, 8, 15, and 22 for Cycle 1 and Days 1, 8, 15, 22, and 28 for Cycle 2. Patients qualifying for Cycle 3 will have visits on Days 1, 8, 15, 22, and 28 of this cycle.

During the first two 28-day cycles, patients will receive a total of 8 infusions: each 28-day cycle will consist of a MOR00208 infusion on Day 1, Day 8, Day 15 and Day 22 of the cycle.

- Patients with a response of at least SD on Cycle 2, Day 28, will qualify for 1 further cycle of MOR00208 (infusions on Day 1, Day 8, Day 15 and Day 22 of the 28-day cycle). This potential Cycle 3 should start 2 weeks \pm 1 day after Cycle 2, Day 22.

Before dosing, premedication as detailed in [Section 9.5](#) should be administered.

Clinical assessments, physical examinations and laboratory evaluations (instead of emergency lab) may be performed within 24 hours before administration of MOR00208 (except PK and anti-MOR00208 antibodies); assessments for Cycle 3 should only be performed if patient qualifies for the respective study drug administration:

- Assessment of AEs and concomitant medication at all visit days (see [Section 9.8](#))
- Assessment of body weight at all visit days
- Physical examination including palpable tumor assessment, general appearance, skin, head, eyes, ears, nose, throat, lungs, breasts and axillae (if applicable including bi-dimensional measurement of cervical, supraclavicular, axillary and inguinal lymph nodes), cardiovascular system, back and spine, abdomen (if applicable including spleen size below the costal margin), extremities, infusion site, lymph nodes and neurological examination at Day 1 (predose) and Day 22 of Cycle 1; and Day 28 of Cycles 2 and 3.
- ECOG performance status (Day 1 and 15 of Cycles 1 to 3)

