3. STUDY METHODS

3.1 Overall Study Design and Plan

This is a Phase IIa open-label, multicenter safety and efficacy study of MOR00208, that will enrol approximately 40 to 120 adult patients with refractory or relapsed NHL who have received at least 1 prior therapy containing rituximab.

The study will enrol patients from four different NHL subtypes: FL, DLBCL, MCL and other indolent NHL (MZL, MALT, etc). Data from the four subtypes will be presented separately, and data will also be presented for FL and other indolent NHL combined, and for all subtypes combined.

The study will employ a two-stage design where the decision to further enrol any NHL subtype in Stage 2 will depend on responses after 2 cycles in Stage 1.

Stage 1: Ten patients per NHL subtype (a minimum of 40 patients in total) will be enrolled to receive MOR00208 12 mg/kg weekly for 8 weeks. After 8 weeks of dosing, patients will be evaluated for response. If fewer than 2 of 10 patients per NHL subtype have a response of PR or better, then continued enrolment in that cohort will be stopped for futility. If at least 2 of 10 patients per NHL subtype have a response of PR or better, then additional patients will be enrolled into Stage 2 for that subtype cohort.

Any patients with a response of at least stable disease (SD) in Stage 1 will qualify for a further 4 weeks of dosing.

Stage 2: An additional 20 patients will be enrolled for each NHL cohort demonstrating a response in Stage 1. After 8 weeks, the ORR will be evaluated for each NHL cohort.

Any patients with a response of at least stable disease (SD) in Stage 2 will qualify for a further 4 weeks of dosing.

Patients who withdraw or discontinue before having received study drug on Cycle 2 Day 22 will only be replaced if the reason for withdrawal/discontinuation was not lack of efficacy.

Patients will not be replaced after they have received treatment for Cycle 2 Day 22, regardless of the reason of withdrawal or discontinuation.

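### SAP 8.1 defines Cycle 3 entrants as PR or CR and non-entrants as PD or SD, contradicting the at-least-SD rule in SAP 3.1 and the protocol; the disposition counts are wrong if programmed from those definitions

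*SAP*

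**What the plan says.** Two rows of the disposition list in SAP 8.1 divide the patients who complete Cycle 2. One is "Number of patients completing the first 2 Cycles without proceeding to Cycle 3 (i.e., PD or SD at the end of Cycle 2"), to be shown with the reason for stopping. The other is "Number of patients who completed Cycle 2 and entered Cycle 3 (i.e., patients who reached PR, or CR by the end of Cycle 2"). A later row in the same list is "Number of patients who discontinued in Cycle 3 (considering all discontinuations that happened in Cycle 3", including those at the end of that cycle); it carries no response condition.

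The treatment rule elsewhere has a different threshold. SAP 3.1 says of Stage 1: "Any patients with a response of at least stable disease (SD) in Stage 1 will qualify for a further 4 weeks of dosing". It says of Stage 2: "Any patients with a response of at least stable disease (SD) in Stage 2 will qualify for a further 4 weeks of dosing". Protocol 10.2 says: "Patients with a response of at least SD on Cycle 2, Day 28, will qualify for 1 further cycle of MOR00208". The protocol synopsis, under statistical methods, says: "Those with SD after Day 28 of the second cycle will be allowed to continue treatment into a third cycle". The schedule of assessments in protocol section 10 heads the column "Cycle 3 (if response is at least SD"). Protocol 7.1 gives the same rule for both stages.

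A threshold of PR or better does appear in the protocol (sections 7.1 and 10.3), but it governs maintenance treatment after Cycle 3, not entry to Cycle 3.

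**The concern.** The two parentheses put SD on the opposite side of the Cycle 3 boundary from the rest of the SAP and the protocol. A patient with SD who receives Cycle 3 meets the heading of the entry row but not its definition. The same patient meets the definition of the non-proceeding row but not its heading.

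In a single-arm study, the disposition table is where a reader sees who continued treatment and why others stopped. If the definitions are programmed, patients who went on to further dosing appear as having ended after Cycle 2, in a row that asks for a discontinuation reason they do not have at that point.

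**Working it through.** The SAP states no figure to reproduce, so the check sets the rules side by side and then follows the counts algebraically.

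**Response at the end of Cycle 2 and where each place puts the patient**

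| Response | SAP 8.1 parentheses | SAP 3.1; protocol 1, 7.1, 10, 10.2 |
|---|---|---|
| CR or PR | entered Cycle 3 | qualifies for Cycle 3 |
| SD | did not proceed | qualifies for Cycle 3 |
| PD | did not proceed | does not qualify |
| Missing | neither row | no placement stated |

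Missing is a response category that the SAP itself recognises (section 7.3.4.1).

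**Possible explanations**

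- *Version difference.* The SAP was written to protocol Amendment 4, and the protocol supplied is Amendment 5. This does not explain the conflict, because SAP 3.1 and SAP 8.1 disagree within one document.
- *Deliberate change.* SAP section 12 lists the changes from the planned analysis. This is not among them.
- *Damaged text.* Both parentheses are intact, and they agree with each other in placing SD among non-entrants.

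**Effect on the counts if the parentheses are programmed**

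Among patients who complete Cycle 2 with a known response, let

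- r = CR or PR, received Cycle 3
- u = CR or PR, did not receive Cycle 3
- s = SD, received Cycle 3
- t = SD, did not receive Cycle 3
- p = PD, did not receive Cycle 3

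By actual dosing: entered = r + s; did not proceed = u + t + p.

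By the parentheses: entered = r + u; did not proceed = s + t + p.

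Error in the entry row = (r + u) − (r + s) = u − s. Error in the non-proceeding row = (s + t + p) − (u + t + p) = s − u.

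The two errors cancel. Both versions sum to r + s + t + u + p, so checking that the rows add up to the Cycle 2 completers would not reveal the fault.

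**Reconciliation with other output**

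- The Cycle 3 discontinuation row counts events in Cycle 3 whatever the response, so it draws on r + s. The entry row by parentheses is r + u. Whenever s > 0, the former includes patients absent from the latter, and it could exceed it.
- The row for discontinuation in Cycle 1 or 2, which includes stops at Cycle 2 Day 28, also has no response condition. It would not contain the s patients whom the non-proceeding row shows as having stopped.
- SAP 11.6 summarises patients by number of cycles completed, from recorded infusions. SD patients who complete three cycles appear there but not in the entry row.

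**Size**

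The documents give neither s nor u. s lies between 0 and the number of SD patients who complete Cycle 2.

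**The case against.** The strongest reply is that each row is headed by a fact of conduct: the patient entered Cycle 3 or did not. On that view the parenthesis is only a gloss, and a programmer working from dosing records would produce correct counts. This stands as a limit: the miscount is conditional on the parentheses being programmed. It does not remove the fault, because the parentheses are introduced as definitions and the text as it stands supports two different tables.

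Second, SD only qualifies a patient for Cycle 3. An SD patient who stops after Cycle 2 for another reason belongs in the non-proceeding row, which is the term t above. That also stands. The error is narrower than any mention of SD in that row: SD is left out of the entry definition, and the other definition reads as if no SD patient proceeds.

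Three stronger readings are tempting, and the documents do not support them:

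- *Cycle 3 exposure would be understated.* It would not. The exposure variables in SAP 7.3.5 come from drug administration recorded in the eCRF for Cycles 1 to 3 and do not use these rows. Only the count of Cycle 3 entrants in the disposition table can be too low.
- *Discontinuation would be overstated throughout the table.* Only the non-proceeding row is exposed. The other discontinuation rows have no response condition and are right under either reading.
- *A number of patients per cohort can be stated.* A reader might apply an assumed SD share to a cohort of 30. No section gives an SD rate; these rows cover only patients who completed Cycle 2; not every SD patient need continue; and a cohort stopped for futility has about 10 patients.

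**Conclusion.** The point holds as an inconsistency that is wrong as written. The response-based definitions of two disposition rows in SAP 8.1 contradict SAP 3.1 and the protocol, and the sections must be reconciled.

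If the definitions are programmed, all SD patients dosed in Cycle 3 are counted as not proceeding. The misplacement is therefore up to the number of such patients, and it is zero if the rows are built from actual dosing. A smaller opposite error arises from any CR or PR patient who did not receive Cycle 3, and patients with a missing end-of-Cycle-2 response fall in neither row.

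The consequence is confined to the disposition table and its agreement with the exposure summary. ORR, DoR, TTP and PFS are derived from response and survival data and do not use these rows. This is a low-severity point, worth correcting because the repair costs almost nothing.

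**What to change.** Reconcile SAP 8.1 with SAP 3.1 and the protocol by deleting the two response-based parentheses. Define both rows by conduct: among patients completing Cycle 2, entered Cycle 3 means at least one Cycle 3 infusion on the eCRF drug administration page, and not proceeding means none. SAP 7.3.5 already derives the number of infusions per cycle, so entry is that count being at least 1 for Cycle 3.

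Within each row, tabulate the end-of-Cycle-2 response as CR, PR, SD, PD or missing. This shows how response relates to continuation without using response to define it, and it gives patients with no assessment a place. Keep the reason for stopping in the non-proceeding row.

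The cost is a short edit to two lines of the SAP and a small change to one table shell. It needs no new data and no change to any efficacy analysis.

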8.2 Protocol Violations and Deviations

Protocol violations and deviations will be defined in the document “Handling of Protocol Non-Compliances”, current version. Protocol non-compliances (PNCs) will be categorized into minor, major or critical. The final decision on a PNC category will be taken based on data listings during data review meetings. Critical and major PNCs will be listed in the CSR and further grouped:

- PNCs related to subjects not satisfying the study entry criteria
- PNCs related to subjects who developed treatment discontinuation criteria during the study but were not withdrawn
- PNCs related to subjects receiving the wrong treatment or incorrect dose
- PNCs related to subjects receiving an excluded concomitant treatment
- Other critical or major PNCs

8.3 Demographics and Other Baseline Characteristics

Descriptive summaries of the demographic and other baseline characteristics will be completed for the populations specified above.

Descriptive summaries of demographic and other baseline conditions will include:

- Demographics (age [both as continuous variable and as number of patients aged < 65 and aged ≥ 65], gender, race, height, weight at screening, body mass index [BMI])
- History of NHL (time since first diagnosis [months], NHL subtype, current staging)
- Medical history
- Previous NHL therapies (see section 7.3.1)
- Scores and categories on prognostic indices (see section 7.3.2)
- ECOG performance status at screening

Statistical Analysis Plan Final Version 4.0

- CD16 expression on NK cells
- Cytogenetics (tumor biopsy)
- DNA analysis of FcγR polymorphism (Mucosal cheek swab)
- Previous and concomitant medication

Medical History: Medical history will be coded with Medical Dictionary for Regulatory Activities (MedDRA Version 20.1). Incidences of findings in medical history will be summarized by system organ class (SOC) and preferred term

Time since first diagnosis of NHL [months]: Time since first diagnosis will be measured from date of first diagnosis until Screening Visit. If date of diagnosis is incomplete, time since first diagnosis [months] will be calculated based on the latest possible date for date of diagnosis:

- If the day is missing but the month is complete for date of diagnosis, the date will be imputed using day 15 of the month (or the date of screening visit in case this is earlier)
 - If the day and month are missing but the year is complete for date of diagnosis, the date will be imputed using June 30 of the year
- DNA analysis of FcγR polymorphism (mucosal cheek swab):* The frequency of each genotype will be summarized descriptively in a frequency table.

Prior and Concomitant medication/ therapies: All medications (prior and concomitant) and all concomitant non-drug therapies will be listed. Any prior, concomitant, or procedural medications or therapy given to or taken by the patient within 1 month before the study and up to the first follow-up visit must be recorded in the source document and the eCRF along with the indication and dosage.

Medications will be presented as prior and concomitant medications.

All medications will be coded using the WHO Drug Dictionary (March 2018). Incidences of prior and concomitant medications will be summarized by ATC level 2 and ATC level 4.

If the start date of medication is before the start date of study treatment the medication will be classified as prior medication.

Medications applied after start of study treatment will be considered as concomitant medication. Medications started before start of study treatment but are ongoing or have a stop date after the start of study treatment will be considered twice, as prior and as concomitant medications. If the start/stop dates of medication are partially or completely missing a medication will be assumed to be concomitant if it cannot be definitely shown that the medication was not administered during the treatment or follow-up period. Missing dates will

not be replaced.

Thus, the following approach will be taken for exclusion from concomitant medication because of discontinuation before start of treatment:

- If stop day is missing but month is complete, medication will only be excluded from concomitant medication if stop month is before month of treatment start.
- If stop day and month are missing but year is complete, medication will only be excluded from concomitant medication if stop year is before year of treatment start.
- If stop date is completely missing, medication will not be excluded

Additionally, concomitant medication will be split into the following two subcategories: (1) concomitant medication started before start of study treatment (and continued after start of study treatment) and (2) concomitant medication started after start of study treatment.

Summary tables of concomitant medication will also be prepared within these two subcategories.

Anti-cancer Treatments: Starting from the first follow-up visit, only anti-cancer treatments and, in case of an AE, other relevant concomitant medications (according to the discretion of the investigator) should be entered to the concomitant medication eCRF module. If a patient receives anti-cancer treatment other than MOR00208, it is regarded as protocol non-compliance. Introduction of new anti-cancer treatment should result in exclusion of the patient from further study participation.

A medical review of the concomitant medication will be performed by [REDACTED] Medical Monitor and approved by MorphoSys Clinical Program Leader before the statistical analysis to identify anti-cancer treatments not allowed during study. All anti-cancer treatments not allowed during study will be included in the protocol violation/deviation listing and table.

The effect of anti-cancer treatments on the efficacy endpoints is described in section 7.3.4.

Previous NHL Therapies:

Information should be provided separately on any previous NHL-specific therapies since the time point of the first diagnosis of NHL. The generic or the trade name or chemo-regimen acronym may be recorded. The previous NHL therapies will be reviewed and assessed for previous lines of therapy, number of systemic therapies, type of previous therapy and rituximab-containing regimens (see section 7.3.1).

